## 2 STUDY DESIGN

### 2.1 Introduction

STAR-0215-201 is a multicenter, single- and multiple-dose study to assess the safety, tolerability, clinical activity, PK, PD, and immunogenicity of STAR-0215 in participants with Type I or Type II HAE. STAR-0215 is a humanized IgG1 kappa light mAb, designed to be a highly potent and specific inhibitor of plasma kallikrein, with a YTE-modified Fc domain to enable delayed clearance and prolonged time in circulation. The study design is a standard approach to the evaluation of the safety and tolerability of an investigational product.

Properly consented participants will undergo screening assessments according to the inclusion and exclusion criteria (Protocol Section 5.1 and Section 5.2, respectively) and immediately enter the Run-In period. During the Run-In period, HAE attack information will be collected to determine if a participant meets the eligibility requirement of experiencing at least 2 HAE attacks during this time period and to establish a baseline prior to STAR-0215 administration. If a participant has an HAE attack during the Run-In period before Day 1 (first dose of STAR-0215), all signs and symptoms of the HAE attack must be resolved before dosing. A washout period for on-demand treatment is not required. The Run-In period may be extended after consultation with the Medical Monitor. In Cohorts 2 and 3, if a participant has an HAE attack immediately before the second dose (Day 84 and Day 28, respectively), signs and symptoms of the HAE attack should be improving per participant report prior to STAR-0215 administration; a washout period for on-demand treatment is not required before the second dose is administered.

In Cohort 1, each participant who has completed the Run-In period and is eligible for STAR-0215 administration will receive 1 dose of STAR-0215 on Day 1. When Cohort 1 has completed dosing, the [Safety Review Committee \(SRC\)](#) will review the cohort's cumulative safety data from the Screening/Run-In period through 21 days after dosing. Progression to Cohort 2 dosing will occur if there are no concerning safety signals. (Protocol Section 4.2)

In Cohort 2, each eligible participant will receive 2 doses of STAR-0215, the first on Day 1 and the second on Day 84. [REDACTED]

In Cohort 3, each eligible participant will receive 2 doses of STAR-0215, the first on Day 1 and the second on Day 28.

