# The value of Tau used for this analysis is 168 days

#### Cohort 2 Dose 1:

Parameter (Units)	CDISC TERM	Definition	Method of Determination
AUC0-84	AUCINT	The area under the curve (AUC) over the interval from 0 to 84 day.	Calculated using the linear up/log down variant of the trapezoidal rule
Cmax	CMAX	maximum observed plasma concentration	Observed value
tmax	TMAX	time to reach Cmax	Observed value

Cavg #	CAVG	Average Concentration	AUCTAU divided by TAU
-------------------	------	-----------------------	-----------------------

#The value of Tau used for this analysis is 56 days

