**Cohort 2 Dose 2:**

Parameter (Units)	CDISC TERM	Definition	Method of Determination
AUC84-251	AUCINT	The area under the curve (AUC) over the interval from 84 to 251 day.	Calculated using the linear up/log down variant of the trapezoidal rule
AUC0-251	AUCINT	The area under the curve (AUC) over the interval from 0 to 251 day.	Calculated using the linear up/log down variant of the trapezoidal rule
AUC0- $\infty$	AUCIFP	Area under the concentration versus time curve from 0 to infinity	Calculated as AUC0-last + Cest,last/ $\lambda_z$ , where Cest,last is the estimated last measurable concentration and AUC0 last is the area under the concentration-time curve from 0 to the time of the last quantifiable (above LLOQ) sample after dosing (calculated using the 'linear up, log down' calculation method )
Cmax	CMAX	maximum observed plasma concentration	Observed value
tmax	TMAX	time to reach Cmax	Observed value
Cavg #	CAVG	Average Concentration	AUCTAU divided by TAU
CL/F *	CLFP	total clearance	Calculated as CLFP = Dose/ AUC0- $\infty$

$t_{1/2}$	LAMZHL	apparent terminal half-life	$\ln(2)/\lambda_z$ , where $\lambda_z$ is the apparent first-order terminal elimination rate constant. At least three consecutive time points (excluding $C_{max}$ ) in the terminal phase will be used for apparent terminal half-life determination, with an $R^2$ value of 0.85 or greater
-----------	--------	-----------------------------	-----------------------------------------------------------------------------------------------------------------------------------------------------------------------------------------------------------------------------------------------------------------------------------------------

\*Computed using the AUC(0-inf) over both doses

#The value of Tau used for this analysis is 168 days

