**Cohort 3 Dose 2:**

Parameter (Units)	CDISC TERM	Definition	Method of Determination
AUC0-195	AUCINT	The area under the curve (AUC) over the interval from 0 to 195 day.	Calculated using the linear up/log down variant of the trapezoidal rule
AUC28-195	AUCINT	The area under the curve (AUC) over the interval from 28 to 195 day.	Calculated using the linear up/log down variant of the trapezoidal rule

AUC 0-∞	AUCIFP	Area under the concentration versus time curve from 0 to infinity	Calculated as AUC 0-last + C est,last /λ z , where C est,last is the estimated last measurable concentration and AUC 0 last is the area under the concentration-time curve from 0 to the time of the last quantifiable (above LLOQ) sample after dosing (calculated using the 'linear up, log down' calculation method )
C max	C MAX	maximum observed plasma concentration	Observed value
t max	T MAX	time to reach C max	Observed value
C avg #	CAVG	Average Concentration	AUCTAU divided by TAU
CL/F *	CLFP	total clearance	Calculated as CLFP = Dose/ AUC 0-∞
t 1/2	LAMZHL	apparent terminal half-life	ln(2)/ λ z , where λ z is the apparent first-order terminal elimination rate constant. At least three consecutive time points (excluding C max ) in the terminal phase will be used for apparent terminal half-life determination, with an R  vale of 0.85 or greater

#The value of Tau used for this analysis is 195 days

\*CL/F computed over the entire time-course of concentrations

In addition to summarization by cohort and dose, the calculated PK parameters will also be summarized by ADA status and dose cohort provided in the dataset. A participant will be considered ADA-positive if, at any time during the dosing interval, anti-drug antibodies are detected. Similarly, treatment-emergent ADA status will be used to summarize PK parameters.

PK parameters will also be summarized graphically by ADA status and dose cohort with either box plots or scatter plots depending on the amount of data.

The AUC parameters will be calculated using the linear trapezoidal method for ascending concentrations and the log trapezoidal method for descending concentrations ('linear up, log down') calculation method option in WinNonlin.

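### Cavg for Cohort 2 Dose 1 is averaged over 56 days although Dose 2 is on Day 84, and Cavg under Dose 2 covers different windows in Cohorts 2 and 3

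*SAP*

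**What the plan says.** SAP section 6.5.1 (Non-Compartmental Analysis) has one parameter table per cohort and dose. Wherever Cavg appears, its method is the same: "AUCTAU divided by TAU". A footnote under each table gives Tau.

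- **Cohort 1:** 168 days.
- **Cohort 2 Dose 1:** "The value of Tau used for this analysis is 56 days". The only AUC in this table is described as "The area under the curve (AUC) over the interval from 0 to 84 day".
- **Cohort 2 Dose 2:** "The value of Tau used for this analysis is 168 days". The table lists a post-Dose-2 AUC, "The area under the curve (AUC) over the interval from 84 to 251 day", and a whole-course AUC from 0 to 251. CL/F is computed over both doses.
- **Cohort 3 Dose 1:** no Cavg is listed.
- **Cohort 3 Dose 2:** "The value of Tau used for this analysis is 195 days". The table lists a whole-course AUC, "The area under the curve (AUC) over the interval from 0 to 195 day", and a post-Dose-2 AUC from 28 to 195. CL/F again covers the whole course.

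On dosing, SAP section 2.1 says: "In Cohort 2, each eligible participant will receive 2 doses of STAR-0215, the first on Day 1 and the second on Day 84". The PK sampling list at the start of section 6.5.1 includes a pre-dose sample on Day 84. No table states where AUCTAU starts, or whether it is one of the listed AUCs.

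**The concern.** Tau in an average-concentration calculation normally means the dosing interval. In Cohort 2 Dose 1 that interval runs from Day 1 to Day 84, and the table's own AUC covers it. A Tau of 56 days matches neither. It coincides only with the Day 56 visit, and no reason is given.

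The second issue is the Dose 2 tables. Cohorts 2 and 3 are both sampled to the same time after Dose 2, so one definition would serve both, yet Tau is 168 days in one and 195 in the other. Because the start of AUCTAU is not stated, the analyst must guess which window is meant.

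At stake is the reading of the PK tables. Protocol section 2.3 says visits are timed so that the profiles after the first and second dose can be compared. Section 2.4 expects the Cohort 3 regimen to give higher concentrations in follow-up. Someone using Cavg for either purpose would be comparing averages over different windows. SAP section 6.5.1 also summarises PK parameters by ADA status, so the same ambiguity carries into those tables.

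**Working it through.** **Step 1. Elapsed days.** SAP section 5.2 has no Day 0, so Day 1 is time zero.

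| Window | Elapsed days | Stated Tau |
|---|---|---|
| Cohort 1, Day 1 to 168 | 168 − 1 = 167 | 168 |
| Cohort 2, Day 1 to 84 | 84 − 1 = 83 | 56 |
| Cohort 2, Day 84 to 251 | 251 − 84 = 167 | 168 |
| Cohort 3, Day 28 to 195 | 195 − 28 = 167 | (195) |
| Cohort 3, Day 1 to 195 | 195 − 1 = 194 | 195 |

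The Tau of 168 agrees with its window to within one day in Cohort 1 and in Cohort 2 Dose 2. The Tau of 195 agrees with the Cohort 3 whole course to within one day, but not with the 167-day post-Dose-2 window. The Tau of 56 reproduces no dosing or AUC interval. It leaves out 83 − 56 = 27 of 83 days, or 33%.

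**Step 2. Effect of averaging over 56 days in Cohort 2 Dose 1.** The documents give no human half-life, so this rests on an assumed model: one compartment, first-order absorption, linear kinetics, half-life 30 to 120 days, absorption rate ka 0.15 to 0.7 per day. With k = ln 2 / half-life, the AUC to time T per unit dose is

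A(T) = ka/(ka − k) × [(1 − e^(−kT))/k − (1 − e^(−ka·T))/ka].

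The ratio of interest is [A(56)/56] / [A(83)/83]. Dose and bioavailability cancel.

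Example with half-life 60 days and ka 0.3: k = 0.01155, A(56) = 39.42 and A(83) = 52.05. The averages are 39.42/56 = 0.704 and 52.05/83 = 0.627, and their ratio is 1.122.

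| Half-life (days) | Ratio at ka 0.15 | Ratio at ka 0.7 |
|---|---|---|
| 30 | 1.212 | 1.252 |
| 60 | 1.097 | 1.136 |
| 90 | 1.053 | 1.090 |
| 120 | 1.030 | 1.066 |

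Over the whole range the 56-day Cavg is 3% to 25% above the 83-day average. The excess shrinks as the half-life grows.

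**Step 3. Effect of the two Dose 2 conventions.** In Cohort 3 the two doses are equal and 27 days apart. Per unit dose:

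- whole-course average = [A(194) + A(167)]/194
- post-Dose-2 average = [A(194) − A(27) + A(167)]/167.

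Their ratio runs from 0.94 (half-life 120, ka 0.15) to 1.11 (half-life 30, ka 0.7). The whole-course value can therefore lie on either side of the post-Dose-2 value, depending on kinetics that the documents do not report.

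**Step 4. Other ways to read AUCTAU.** These are conditional.

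- Dividing the listed 0-to-84 AUC by 56 would inflate Cavg by 83/56 = 1.48, or 84/56 = 1.50 on nominal days.
- Dividing the listed 28-to-195 AUC by 195 would give 167/195 = 0.856 of the right value, 14% low.
- Counting 195 days from Dose 2 would end on Day 28 + 195 = 223, which is 28 days after the last PK sample.

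**The case against.** **The average is right for its own window.** If AUCTAU is integrated over the stated Tau, each Cavg is a correct average. The SAP leans this way: the listed interval AUCs carry the CDISC term AUCINT, while Cavg refers to AUCTAU, and nothing makes one the numerator of the other. This stands. A reader might infer from Step 4 that Cavg is 48% to 50% too high in Cohort 2 or 14% too low in Cohort 3. The documents do not support that, because nothing in them says a listed AUC is to be divided by a Tau of another length.

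**195 days is not an error.** A reader might also take the Cohort 3 Tau for an arithmetic mistake. It matches the whole-course AUC listed in the same table, and CL/F there is also whole-course. This stands too. It does not settle comparability, since Cohort 2 Dose 2 also lists a whole-course AUC and a CL/F over both doses, yet sets Tau to 168 days. The same parameter under the same heading follows two conventions.

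**56 days may follow the sampling list.** That list groups samples up to Day 56 under the first dose and puts the Day 84 pre-dose sample under the second. This may be where the number came from, but the SAP does not say so. The Day 84 pre-dose sample closes the first interval, and the 0-to-84 AUC in the same table needs it.

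**Cavg carries little weight.** It is not among the PK parameters listed in SAP section 3.3 or Protocol section 9.5. No Cavg comparison between doses or cohorts is specified, and the 84-to-251 and 28-to-195 AUCs already give matched post-Dose-2 exposure. This stands and limits the importance of the point.

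**Conclusion.** The point holds in two parts.

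First, the 56-day Tau in Cohort 2 Dose 1 conflicts with the SAP's own dosing day, AUC interval and sampling. Followed as written, it yields an average over the first 56 days, about 3% to 25% above the full-interval average. The size depends on the assumed model and half-life. The conflict itself needs no assumption.

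Second, the Dose 2 Cavg values in Cohorts 2 and 3 cover different windows, and the start of AUCTAU is not stated. They are not comparable as specified. If Cohort 3 is whole-course, its Cavg is 0.94 to 1.11 times its post-Dose-2 equivalent under the same assumptions.

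This is a specification fault in one descriptive PK parameter. SAP section 6.2.1 plans no formal hypothesis testing, so no inferential result changes.

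**What to change.** - **Cohort 2 Dose 1:** set Tau to the interval from Dose 1 to Dose 2 (83 elapsed days, 84 nominal), with AUCTAU over exactly that interval.
- **Dose 2, Cohorts 2 and 3:** report a post-Dose-2 Cavg in both over the same window, using the 84-to-251 and 28-to-195 AUCs (167 elapsed days each).
- **Whole-course averages:** if wanted, report them for both cohorts (0 to 251 and 0 to 195) under a separate name.
- **All Cavg footnotes:** state the start and end of AUCTAU, and apply one day-count convention throughout, including the two 168-day footnotes, which stand for 167 elapsed days.

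The cost is a few SAP footnotes and the matching settings in the PK software. No new data or visits are needed. Any Cavg tables already produced with the 56-day or 195-day settings should be rerun or relabelled.

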**Cohort 2 Dose 2:**

Parameter (Units)	CDISC TERM	Definition	Method of Determination
AUC84-251	AUCINT	The area under the curve (AUC) over the interval from 84 to 251 day.	Calculated using the linear up/log down variant of the trapezoidal rule
AUC0-251	AUCINT	The area under the curve (AUC) over the interval from 0 to 251 day.	Calculated using the linear up/log down variant of the trapezoidal rule
AUC0- $\infty$	AUCIFP	Area under the concentration versus time curve from 0 to infinity	Calculated as AUC0-last + Cest,last/ $\lambda_z$ , where Cest,last is the estimated last measurable concentration and AUC0 last is the area under the concentration-time curve from 0 to the time of the last quantifiable (above LLOQ) sample after dosing (calculated using the 'linear up, log down' calculation method )
Cmax	CMAX	maximum observed plasma concentration	Observed value
tmax	TMAX	time to reach Cmax	Observed value
Cavg #	CAVG	Average Concentration	AUCTAU divided by TAU
CL/F *	CLFP	total clearance	Calculated as CLFP = Dose/ AUC0- $\infty$

$t_{1/2}$	LAMZHL	apparent terminal half-life	$\ln(2)/\lambda_z$ , where $\lambda_z$ is the apparent first-order terminal elimination rate constant. At least three consecutive time points (excluding $C_{max}$ ) in the terminal phase will be used for apparent terminal half-life determination, with an $R^2$ value of 0.85 or greater
-----------	--------	-----------------------------	-----------------------------------------------------------------------------------------------------------------------------------------------------------------------------------------------------------------------------------------------------------------------------------------------

\*Computed using the AUC(0-inf) over both doses

#The value of Tau used for this analysis is 168 days

**Cohort 3 Dose 1:**

Parameter (Units)	CDISC TERM	Definition	Method of Determination
AUC0-28	AUCINT	The area under the curve (AUC) over the interval from 0 to 28 day.	Calculated using the linear up/log down variant of the trapezoidal rule
$C_{max}$	C MAX	maximum observed plasma concentration	Observed value
$t_{max}$	T MAX	time to reach $C_{max}$	Observed value

**Cohort 3 Dose 2:**

Parameter (Units)	CDISC TERM	Definition	Method of Determination
AUC0-195	AUCINT	The area under the curve (AUC) over the interval from 0 to 195 day.	Calculated using the linear up/log down variant of the trapezoidal rule
AUC28-195	AUCINT	The area under the curve (AUC) over the interval from 28 to 195 day.	Calculated using the linear up/log down variant of the trapezoidal rule

AUC 0-∞	AUCIFP	Area under the concentration versus time curve from 0 to infinity	Calculated as AUC 0-last + C est,last /λ z , where C est,last is the estimated last measurable concentration and AUC 0 last is the area under the concentration-time curve from 0 to the time of the last quantifiable (above LLOQ) sample after dosing (calculated using the 'linear up, log down' calculation method )
C max	C MAX	maximum observed plasma concentration	Observed value
t max	T MAX	time to reach C max	Observed value
C avg #	CAVG	Average Concentration	AUCTAU divided by TAU
CL/F *	CLFP	total clearance	Calculated as CLFP = Dose/ AUC 0-∞
t 1/2	LAMZHL	apparent terminal half-life	ln(2)/ λ z , where λ z is the apparent first-order terminal elimination rate constant. At least three consecutive time points (excluding C max ) in the terminal phase will be used for apparent terminal half-life determination, with an R  vale of 0.85 or greater

#The value of Tau used for this analysis is 195 days

\*CL/F computed over the entire time-course of concentrations

In addition to summarization by cohort and dose, the calculated PK parameters will also be summarized by ADA status and dose cohort provided in the dataset. A participant will be considered ADA-positive if, at any time during the dosing interval, anti-drug antibodies are detected. Similarly, treatment-emergent ADA status will be used to summarize PK parameters.

PK parameters will also be summarized graphically by ADA status and dose cohort with either box plots or scatter plots depending on the amount of data.

The AUC parameters will be calculated using the linear trapezoidal method for ascending concentrations and the log trapezoidal method for descending concentrations ('linear up, log down') calculation method option in WinNonlin.

Onset of the apparent terminal log-linear phase used in the calculation of  $\lambda_z$  will be determined using WinNonlin Auto Selection and will be reviewed by the pharmacokineticist for reasonableness. No values for AUC0-∞ or Apparent Terminal t1/2 will be reported for cases that do not exhibit a terminal log-linear phase in the concentration versus time profile.

Parameters "Rsquared\_adjusted" (adjusted R^2), AUC0-last, and "AUC%extrap\_predicted" (predicted percent extrapolated AUC0-∞) will be included as part of WinNonlin parameter output for supportive information on determination of the individual Apparent Terminal t1/2 and AUC0-∞ values. For half-life, only estimates with a minimum of 3 time-points and an R^2 value of 0.85 or greater will be reported.

All PK parameters will be listed by participant and summarized by cohort. The following descriptive statistics will be presented: n (number of non-missing observations), arithmetic mean, SD, median, Q1, Q3, minimum, maximum, geometric mean, geometric CV). Geometric CV (GCV) will be calculated as  $GCV\% = \sqrt{\exp(s^2) - 1} \times 100$  and s is the standard deviation of the log-transformed values.

The PK parameters like AUC and Cmax will be represented in 3 significant digits and Tmax (individual, MIN, MED and MAX) in 2 decimals. The descriptive statistics like AM, SD, GM, MED, MIN, MAX will be represented in 3 significant digits and ACV, GCV in 1 decimal. For individual concentration summary stats, IQR will be represented in 3 significant digits.

If the pre-dose (before first dose) concentration at Visit 1 is  $\leq 5\%$  of Cmax value, the participant's data without any adjustment will be included in all pharmacokinetic calculations. If the pre-dose (before first dose) value is  $> 5\%$  of Cmax, the participant will be dropped from all PK calculations and descriptive statistics.

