2.4. Dose Selection Rationale

The starting dose of STAR-0215 for participants with HAE in this study was based on PK/PD modeling. The information evaluated for dose selection for this study included: (1) estimated plasma kallikrein inhibition required for HAE attack suppression based on literature reports ([Section 2.4.1](#)) and (2) human PK models (empirical and minimal physiologically-based PK). Based on the totality of the PK/PD modeling, a single dose of 450 mg was estimated to provide adequate target coverage for HAE attack suppression in participants with HAE for a prolonged duration. Therefore, 450 mg was selected to be the starting dose in this Phase 1b/2 study. The planned dosing regimen for Cohort 2 is 600 mg followed by 300 mg 84 days later. Based on PK/PD modeling, this regimen, in which the initial dose is a loading dose, has the potential to rapidly boost C_{min} concentrations to levels believed to provide robust and durable inhibition of plasma kallikrein that may translate into immediate and sustained clinical reductions in HAE attacks. The planned dosing regimen for Cohort 3 is 600 mg followed by 600 mg 28 days later. This regimen includes an initial loading dose on D1 and a second dose on D28, expected to result in higher STAR-0215 concentrations during the follow-up period. Upon review of emerging data from the ongoing Phase 1a trial and Cohorts 1, 2, and 3 from this trial, [REDACTED] and [REDACTED] in [REDACTED] may be explored.

Single doses of up to and including 1200 mg are being evaluated in the ongoing Phase 1a study in healthy adult participants. Initial clinical PK data from the Phase 1a study support the administration of STAR-0215 in humans at a dose level of at least 1600 mg for SC administration and 1200 mg for IV administration. Please refer to the IB for updated information regarding safety and PK from the Phase 1a study.

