9.5. Pharmacokinetic Analysis

Pharmacokinetic analyses will be conducted on participants in the PK Analysis Set.

Pharmacokinetic parameters will be listed by participant and summarized by dose group using descriptive statistics.

STAR-0215 PK parameters will be computed, when data allow, using standard noncompartmental methods based on observed STAR-0215 concentrations and on actual sample collection times. The following noncompartmental PK parameters, when data allow, will be calculated and reported:

- Maximum drug concentration (C_{\max})
- Time of C_{\max} (T_{\max})
- Area under the curve (AUC) after a defined duration or at steady state
- Circulating half-life ($t_{1/2}$)
- Apparent clearance (CL/F)
- Volume of distribution (V/F)

Individual blood concentrations of STAR-0215 will be plotted by actual time on both linear and semi-logarithmic scales. Mean blood concentrations will be plotted by nominal time and on both linear and semi-logarithmic scales. A preliminary assessment of dose proportionality will be made by examining plots of dose-normalized AUC and C_{\max} values versus the STAR-0215 dose. When data allow, accumulation will be assessed.

Full details of the PK analysis and modeling approach will be provided in the SAP or a separate PK analysis plan as appropriate.

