### 5.3 Methods of Pooling Data

Not applicable.

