### 6.2 General Statistical Methods

#### 6.2.1 General Methods

All outputs will be incorporated into Microsoft Excel or Word files, sorted and labeled according to the International Conference on Harmonization (ICH) recommendations, and formatted to the appropriate page size(s).

Tabulations will be produced for appropriate demographic, baseline, efficacy, PK, PD, Immunogenicity and safety parameters. For categorical variables, summary tabulations of the number and percentage within each category (with a category for missing data) of the parameter will be presented. For continuous variables, the mean, median, standard deviation, Q1, Q3, minimum and maximum values will be presented. The PK summaries will additionally include the percent coefficient of variation (CV%), geometric mean, and geometric CV%. Descriptive statistics for categorical variables will consist of frequency counts and percentages.

Results will be presented by cohort.

No formal statistical hypothesis testing will be performed. Summary statistics will be presented, as well as 95% confidence intervals (CI) on selected parameters, as described in the sections below.

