## 6.5 Pharmacokinetic pharmacodynamics (PD), immunogenicity and biomarkers Variables Evaluations

### 6.5.1 Pharmacokinetic Evaluations

Pharmacokinetic analyses will be conducted on participants in the PK Analysis Set and individual plasma concentration summary statistics will be computed using all available PK data. Assays from LC-MS/MS and ELISA will both be analyzed.

Plasma Concentrations:

Cohort 1:

Day1: Predose, 4hr (post -dose); 2, 7, 14, 28, 56, 84, 112, 140, 168 days post-dose

Cohort 2:

Day1: Predose, 4hr (post -dose); 2, 7, 14, 28, 56 day

Day 84: Predose, 4hr (post -dose); 85, 90, 97, 111, 139, 167, 209, 251 days post-initial dose

Cohort 3:

Day1: Predose, 4hr (post -dose); 2, 7, 14 day

Day28: Predose, 4hr (post -dose); 29, 34, 41, 55, 83, 111, 153, 195 days post-initial dose

Individual plasma STAR-0215 concentration data will be listed for each participant and summarized by nominal sampling time point and visit as applicable with descriptive statistics as described below.

Plasma concentrations below the limit of quantification (BLQ) will be flagged as BLQ in the concentration and parameters tables and considered to be 0 for PK and descriptive statistical analysis. BLQ values in between two measurable concentrations will be treated as missing.

If more than 50% of values are below the LLOQ, the mean and standard deviation will be shown as not calculable (NC), and the minimum value will be shown as BLQ. BLQ values between two measurable concentrations are treated as missing. Missing values will be omitted from the calculation of descriptive statistics. Number of missing values will be reported in descriptive statistics.

Individual plasma concentration-time data will be displayed graphically, summarized, and listed. Individual plasma concentrations below the LLOQ will be graphed as  $\frac{1}{2}$  LLOQ.

Plasma concentrations will be summarized by visit / timepoint including all sample assessments. The following descriptive statistics will be presented for plasma concentrations obtained at each nominal time point. n (number of non-missing observations), arithmetic mean(AM), SD, median, Q1, Q3, minimum, maximum, geometric mean, geometric CV, where  $GCV\% = \sqrt{\exp(s^2) - 1} * 100$  and s is the standard deviation of the log-transformed values.

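### Cohorts 2 and 3 share a 600 mg first dose and the same sampling to Day 28, but the SAP plans no combined first-dose PK or PD summary: a free, minor gain in precision

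*SAP*

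**What the plan says.** Protocol 2.4 gives the two regimens: "The planned dosing regimen for Cohort 2 is 600 mg followed by 300 mg 84 days later", and "The planned dosing regimen for Cohort 3 is 600 mg followed by 600 mg 28 days later". The first dose is the same; the regimens part at Day 28.

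SAP 6.5.1 lists the PK samples after the first dose as "Day1: Predose, 4hr (post -dose); 2, 7, 14, 28, 56 day" for Cohort 2 and "Day1: Predose, 4hr (post -dose); 2, 7, 14 day" for Cohort 3. Cohort 3 then has a Day 28 sample taken before its second dose. The schedules of assessments put PD samples at the same times.

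On presentation, SAP 6.2.1 says "Results will be presented by cohort", SAP 6.5.1 says "All PK parameters will be listed by participant and summarized by cohort", and SAP 5.3, on methods of pooling, reads "Not applicable". The parameter tables in SAP 6.5.1 are laid out by cohort and by dose number within cohort. SAP 6.5.2 adds a within-group p-value for PD at each visit and timepoint.

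Protocol 9.5 says "Pharmacokinetic parameters will be listed by participant and summarized by dose group using descriptive statistics" and plans a preliminary look at dose proportionality from plots of dose-normalised AUC and Cmax against dose.

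**The concern.** Up to the Day 28 sample, participants in Cohorts 2 and 3 have had the same planned dose, under the same eligibility criteria and the same sampling times. The plan nevertheless estimates the response to that dose twice, each time from one small cohort, and never once from all who received it.

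Single-dose PK and PD belong to the secondary objectives (Protocol 3). The only other first-dose level is 450 mg, in 4 participants, so precision left unused at 600 mg matters in any comparison of the two. Two sets of results for one first dose also invite a chance difference to be read as a real one. This applies most to PD, where SAP 6.5.2 would attach separate p-values to the same first-dose state in each cohort.

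A related gap is that the AUC windows after Dose 1 are not the same in any two cohorts, so first-dose AUC cannot be compared across cohorts from the planned outputs.

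**Working it through.** **Plan's own figure.** The cohort maxima add up to 4 + 12 + 12 = 28, the stated maximum (SAP 6.1); the initial sizes give 4 + 6 + 6 = 16. The documents state no SD, CV, power or precision target.

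**Sampling after the first dose** (SAP 6.5.1 and schedules of assessments).
- Cohort 2: pre-dose, 4 h, Days 2, 7, 14, 28, then Day 56 and Day 84 pre-dose.
- Cohort 3: pre-dose, 4 h, Days 2, 7, 14, then Day 28 pre-dose.
- Common part: pre-dose, 4 h, Days 2, 7, 14 and 28, for PK and PD alike.

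**Share of data used.** Share = cohort size / (sum of Cohorts 2 and 3): 6/12 = 50%, 12/24 = 50%; at 12+6, 6/18 = 33% or 12/18 = 67%.

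**Precision.** The standard error ratio, pooled to single cohort, is sqrt(n/N). With equal cohorts it is sqrt(1/2) = 0.707, a 29% reduction. The 95% CI half-width for a mean, in SD units, is t(0.975, n−1)/sqrt(n):

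| Sizes | One cohort | Pooled | Ratio | Narrower by |
|---|---|---|---|---|
| 6+6 | 1.049 (n=6) | 0.635 (n=12) | 0.605 | 39% |
| 12+12 | 0.635 (n=12) | 0.422 (n=24) | 0.665 | 34% |
| 12+6, smaller cohort | 1.049 (n=6) | 0.497 (n=18) | 0.474 | 53% |
| 12+6, larger cohort | 0.635 (n=12) | 0.497 (n=18) | 0.783 | 22% |

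**On the PK scale.** The CI factor for a geometric mean is exp(h·s), with h the half-width above and s = sqrt(ln(1+CV²)). The geometric CV is an assumption, shown over a range:

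| Assumed CV | n=6 | n=12 | n=24 |
|---|---|---|---|
| 20% | ×/÷ 1.231 | ×/÷ 1.134 | ×/÷ 1.087 |
| 30% | ×/÷ 1.361 | ×/÷ 1.205 | ×/÷ 1.132 |
| 50% | ×/÷ 1.642 | ×/÷ 1.350 | ×/÷ 1.221 |

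**PD p-values.** SAP 6.5.2 names no test. As an illustration, the smallest two-sided p-value of an exact signed-rank test is 2/2ⁿ: 0.031 at n = 6 and 0.0005 at n = 12.

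**AUC after Dose 1** (SAP 6.5.1).
- Cohort 1: AUC0-t, to the last quantifiable sample or 168 days, and AUC0-∞.
- Cohort 2: AUC0-84.
- Cohort 3: AUC0-28.

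No first-dose window is shared. AUC0-∞ is defined in all three cohorts, but in Cohorts 2 and 3 it spans both doses, so it relates to cumulative doses of 600 + 300 = 900 mg and 600 + 600 = 1,200 mg. All three cohorts have a Day 28 sample, so AUC0-28 can be derived in each.

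**The case against.** The strongest case against is that by-cohort display is valid, was always intended, and loses little.

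- A reader might infer that the SAP changed the protocol's grouping from dose group to cohort without declaring it. The documents do not support that. Protocol 9.2 already presents results by cohort, and Protocol 9.3 analyses participants by assigned dose cohort. The protocol also uses dose, dose cohort, dose group and treatment group loosely. SAP 7 had nothing to declare on this point.
- A reader might also infer from "Not applicable" in SAP 5.3 that pooling is ruled out. It is a bare entry under a standard heading and says only that no pooling method is specified. Disposition in SAP 6.3.1 is shown by cohort and overall.
- SAP 6.5.1 and 6.5.2 plan no confidence interval for PK or PD, so the narrower intervals describe precision and would not appear in any planned table. This is right, and it limits the weight of the point.
- The cohorts are sequential and not randomised, so a combined column needs a caveat. This stands and is carried into the fix.
- Parameters are listed by participant, so a reader could assemble a 600 mg summary for Cmax and Tmax. Protocol 9.5 also allows a separate PK analysis plan, which is not among the documents. Both points reduce the loss. Neither supplies a planned summary or a common AUC window.
- Decisions on adding participants are made by cohort, so the cohort columns serve their purpose and should stay.

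**Conclusion.** The point holds as a free, minor improvement. Cohorts 2 and 3 share dose and sampling through the Day 28 pre-dose sample, and no combined 600 mg first-dose summary is planned. The loss is precision: a standard error about 29% smaller is available with equal cohorts, equivalent to a 95% CI 39% narrower (6 to 12) or 34% narrower (12 to 24). The by-cohort estimates are not biased.

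It would be too strong to say that half of the data always go unused. That is true only for equal cohorts; at 12+6, each cohort's estimate uses one third or two thirds.

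The AUC gap is separate and also real: without a shared window, the AUC half of the dose-normalised plots cannot compare first doses of 450 mg and 600 mg.

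The SD-unit results assume independent participants and a common mean and SD in the two cohorts through Day 28. The geometric-mean factors also rest on assumed CVs of 20% to 50%, and the p-value floors on a test that the SAP does not name. Half-life, CL/F and AUC0-∞ are unaffected.

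**What to change.** Keep every cohort column, and amend SAP 5.3, 6.5.1 and 6.5.2 as follows.

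1. Add a column, *600 mg first dose (Cohorts 2+3)*, for concentrations, Cmax, Tmax, PD values, change from baseline and % inhibition, through the Day 28 pre-dose sample. If the within-group PD p-values are kept, give them for this column too and name the test.
2. Exclude all Cohort 3 samples taken after Dose 2.
3. Define AUC0-28 for all three cohorts, with a stated rule for Day 28 samples drawn early or late within the ±2-day window. Use it, with Cmax over Days 0-28, in the dose-normalised plots of 450 mg against 600 mg.
4. Footnote that the cohorts were enrolled sequentially and were not randomised.
5. Record the addition in the SAP modification history, since that history shows that interim PK summaries have already been produced.

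The cost is one extra column in the Dose 1 PK and early PD tables and figures, and one extra AUC in Cohorts 1 and 2. No new samples are needed and no planned output is lost.
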